1.3. Schedule of Activities

Table 1. Study Period I -Screening and Randomization

Activity Screening		ening	Randomization	Comments
Visit number	1	2	3	
Week of treatment	-4	-2	0	
Allowable deviation (days)	NA	-7/+3	-3/+7	The visit date after randomization visit is determined in relation to the date of the randomization visit (\pm the allowed visit window).
Fasting visit	X	X	X	If the participant is not fasting, the participant should be called in for a new visit within the visit window. Patients must be fasting at least 10 hours before blood sampling.
Informed consent	X			
Randomization			X	
Medical history	X			
Obesity disease assessment	X			Eleven of obesity-related health problems defined by JASSO will be utilized (Appendix 13, Section 10.13).
Adverse events and product complaints	X	X	X	At Visit 2, this activity can be performed on same day as OGTT test.
Concomitant medications	X	X	X	At Visit 2, this activity can be performed on same day as OGTT test.
Hand out diary, instruct in use			X	All training should be repeated as needed to ensure participant compliance.
Lifestyle management counseling			Х	Counselling on diet and exercise, to be performed by a dietician or equivalent qualified delegate, will include calculation of individualized energy requirement and methods to change dietary composition and amount of physical activity. The lifestyle management counseling may be delivered on a separate day from the rest of that visit's study procedures but must occur within the visit window.
Review diet and exercise goals			X	
Injection training with auto-injector demonstration device			X	
Dispense study drug			X	

Activity	Screening		Randomization	Comments
Visit number	1	2	3	
Week of treatment	-4	-2	0	
Allowable deviation (days)	NA	-7/+3	-3/+7	The visit date after randomization visit is determined in relation to the date of the randomization visit (± the allowed visit window).
Fasting visit	X	X	X	If the participant is not fasting, the participant should be called in for a new visit within the visit window. Patients must be fasting at least 10 hours before blood sampling.
Observe participant administer study drug			X	
Patient-reported outcomes measurements				
SF-36v2, acute form			X	
IWQoL-Lite-CT			X	
EQ-5D-5L			X	
Patient Global Impression of Status			X	
C-SSRS (baseline/screening version)	X			
C-SSRS (since last visit version)		X	X	At Visit 2, C-SSRS can be performed on same day as OGTT test.
PHQ-9	X		X	

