4.1. Overall Design

Study GPHZ is a Phase 3, multicenter, randomized, placebo-controlled, double-blinded study to evaluate the safety and efficacy of subcutaneously administered tirzepatide 10 mg and/or 15 mg QW compared with placebo when used in conjunction with a reduced calorie diet and increased physical activity for weight management, in obesity disease participants with BMI \geq 27 and <35 kg/m² and at least 2 obesity-related health problems or BMI \geq 35 kg/m² and at least 1 obesity-related health problems. The obesity-related health problems are IGT, hyperlipidemia, or NAFLD.

The study population will be enriched for participants who have NAFLD and IGT, such that more than 40% of the total study population will consist of participants with NAFLD, and more than 60% of the total study population will consist of participants with IGT.

Study GPHZ will consist of 3 periods: a 4-week screening period, followed by a 72-week treatment period including a 20-week dose escalation, and a 4-week safety, off-drug, follow-up period. Approximately, 261 participants will be randomized in a 1:1:1 ratio to tirzepatide 10 mg, 15 mg, or placebo.

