- 11. Have a history of significant active or unstable major depressive disorder or other severe psychiatric disorder (for example, schizophrenia, bipolar disorder, or other serious mood or anxiety disorder) within the last 2 years

Note: Participants with major depressive disorder or generalized anxiety disorder whose disease state is considered stable for the past 2 years and expected to remain stable throughout the course of the study, in the opinion of the investigator, may be considered for inclusion if they are not on excluded medications

- 12. Have any lifetime history of a suicide attempt
- 13. Have a Patient Health Questionnaire-9 (PHQ-9) score of 15 or more at Visit 1 or 3, prior to randomization
- 14. On the Columbia-Suicide Severity Rating Scale (C-SSRS) at Visits 1 or 3, prior to randomization:
 - a. a "yes" answer to either Question 4 (Active Suicidal Ideation with Some Intent to Act, Without Specific Plan)

or

b. a "yes" answer to Question 5 (Active Suicidal Ideation with Specific Plan and Intent) on the "Suicidal Ideation" portion of the C-SSRS

c. a "yes" answer to any of the suicide-related behaviors (Actual Attempt, Interrupted Attempt, Aborted Attempt, Preparatory Act or Behavior) on the "Suicidal Behavior" portion of the C-SSRS

and

- d. the ideation or behavior occurred within the past month
- 15. Have any of the following cardiovascular conditions within 3 months prior to randomization:
 - · acute myocardial infarction
 - cerebrovascular accident (stroke)
 - · unstable angina
 - · hospitalization due to congestive heart failure
 - · uncontrolled hypertension (systolic blood pressure above or equal to 160 mmHg and/or diastolic blood pressure above or equal to 100 mmHg)
- 16. Have New York Heart Association Functional Classification IV congestive heart failure
- 17. Have a serum calcitonin level (at Visit 1) of 35 ng/L or more, as determined by central laboratory at Visit 1

- 18. Have a family or personal history of medullary thyroid carcinoma or Multiple Endocrine Neoplasia Syndrome type 2
- 19. Have a history of an active or untreated malignancy or are in remission from a clinically significant malignancy (other than basal- or squamous-cell skin cancer, in situ carcinomas of the cervix, or in situ prostate cancer) for less than 5 years
- 20. Have any other condition not listed in this section (for example, hypersensitivity or intolerance) that is a contraindication to GLP-1R agonists

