8.2.5. Depression, Suicidal Ideation and Behavior Risk Monitoring

Overweight and obese patients are at increased risk for depression (Luppino et al. 2010). Depression can increase the risk for suicidal ideation and behavior. Therefore, study participants will be screened at trial entry and monitored during the study for depression, and suicidal ideation and behavior.

Participants should be monitored appropriately and observed closely for suicidal ideation and behavior or any other unusual changes in behavior, especially at the beginning and end of the course of treatment, or at the time of dose changes, either increases or decreases. Consideration should be given to discontinuing study medication in subjects who experience signs of suicidal ideation or behavior, following a risk assessment (Section 10.4.7.12).

Baseline and treatment-emergent assessment of depression, suicidal ideation and behavior will be monitored during the study using the C-SSRS and PHQ-9 (Section 10.4.7.12).

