# 4.5. Safety Analyses

Unless specified otherwise, safety assessments will be based on the SS (Table GPHZ.3.1). All data collected between randomization and the end date of study participation will be included, regardless of the adherence to study drug.

The statistical assessment of homogeneity of the distribution of categorical safety responses, between tirzepatide doses and placebo, will be conducted using Fisher's exact test, unless specified otherwise.

The mean change from baseline differences among treatments at all scheduled visits will be assessed via an MMRM using REML. Unless specified otherwise, if the safety parameter is assessed at the 72 weeks, then the model will include treatment group, visit and treatment-by-visit interaction and stratification factors as fixed effects, and baseline value of the safety parameter as a covariate. To model the covariance structure within participants, the unstructured covariance matrix will be used. If this model fails to converge, the covariance structures specified in Section 4.3.2.1 will be tested in order until met convergence. If the data does not warrant the MMRM model, then ANCOVA model will be conducted.

For selected safety parameters, time-to-first-event analysis via the Cox-proportional hazards model may be conducted. Participants without the event will be censored at the end of study participation. For participants experiencing the event, the "time-to-first-event" will be the time (in weeks) from first dose to first occurrence of the event.

Where necessary, the rate of events will be analyzed using a generalized linear mixed-effects model, assuming the number of events follow a negative binomial distribution and with treatment as a fixed effect. The logarithm of days during the active treatment period will be adjusted as an offset, to account for possible unequal treatment duration of follow-up among participants.

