## 4.5.5.9.2. Suicidal Ideation and Behavior Solicited Through C-SSRS

Suicide-related thoughts and behaviors occurring during the entire study period, based on the C-SSRS, will be summarized by treatment group. In particular, for each of the following suicide-related events, the counts and percentages of participants with the event will be summarized by treatment group:

- Died by suicide,
- Nonfatal suicide attempt,
- Interrupted attempt,
- Aborted attempt,
- Preparatory acts or behavior,
- Active suicidal ideation with specific plan and intent,
- Active suicidal ideation with some intent to act without specific plan,
- Active suicidal ideation with any methods (no plan) without intent to act,
- Nonspecific active suicidal thoughts,
- Wish to be dead, and
- Non-suicidal, self-injurious behavior.

In addition, the counts and percentages of participants who experienced at least 1 of the composite measures will be presented. The participants with at least 1 postbaseline C-SSRS assessment are included. The composite measure is determined at each assessment by the "yes" or "no" responses in the following C-SSRS categories by the study participant:

- Category 1 Wish to be Dead;
- Category 2 Non-specific Active Suicidal Thoughts;
- Category 3 Active Suicidal Ideation with Any Methods (Not Plan) without Intent to Act;
- Category 4 Active Suicidal Ideation with Some Intent to Act, without Specific Plan;
- Category 5 Active Suicidal Ideation with Specific Plan and Intent;
- Category 6 Preparatory Acts or Behavior;
- Category 7 Aborted Attempt;
- Category 8 Interrupted Attempt;
- Category 9 Actual Attempt (non-fatal);
- Category 10 Completed Suicide.

Composite endpoints of suicidal ideation and suicidal behavior based on the above categories are defined below:

- Suicidal ideation: A "yes" answer at any time during study to any 1 of the 5 suicidal ideation questions (Categories 1-5) on the C-SSRS;
- Suicidal behavior: A "yes" answer at any time during study to any 1 of the 5 suicidal behavior questions (Categories 6-10) on the C-SSRS;
- Suicidal ideation or behavior: A "yes" answer at any time during study to any 1 of the 10 suicidal ideation and behavior questions (Categories 1-10) on the C-SSRS.

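### The C-SSRS composites have no comparison with baseline, so ideation present before dosing and reported again unchanged counts as an event

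*SAP*

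**What the plan says.** SAP section 4.5.5.9.2 opens with the single C-SSRS events: "Suicide-related thoughts and behaviors occurring during the entire study period, based on the C-SSRS, will be summarized by treatment group". It then defines three composites. Ideation is a yes "answer at any time during study to any 1 of the 5 suicidal ideation questions (Categories 1-5) on the C-SSRS". Behavior (Categories 6 to 10) and ideation-or-behavior (Categories 1 to 10) follow the same pattern. The composite denominator is restricted: "The participants with at least 1 postbaseline C-SSRS assessment are included". The numerator carries no such restriction, and no row compares a participant with his or her own baseline.

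Protocol section 8.2.5 sets a different expectation: "Baseline and treatment-emergent assessment of depression, suicidal ideation and behavior will be monitored during the study using the C-SSRS and PHQ-9". Protocol section 9.4.4.4.3 leaves the analysis details to the SAP.

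The Schedule of Activities (protocol section 1.3) places a baseline/screening form at Visit 1 and the since-last-visit form at Visits 2 and 3 and at every later visit. Exclusion criterion 14 removes participants with a yes to Question 4, Question 5 or a suicide-related behavior at Visit 1 or 3, but only if "the ideation or behavior occurred within the past month".

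**The concern.** There are two gaps, the first more important.

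First, the composites do not separate new or worse ideation from ideation that was there before study drug. A participant who answers yes to Category 1, 2 or 3 at screening can be randomized. If that participant gives the same answer after dosing, the table shows an event, with nothing to mark it as unchanged. Neighboring parts of the SAP do make the distinction: PHQ-9 has baseline-to-postbaseline shift tables and three worsening outcomes, adverse events are treatment-emergent only if they first occur or worsen after baseline, and abnormal vital signs need a change from baseline.

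Second, section 4.5.5.9.2 leaves the start of its window open. Table GPHZ.4.1 defines baseline and postbaseline for adverse events, laboratory tests, vital signs and ECGs, but not for the C-SSRS.

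Depression, suicidal ideation or behavior is a listed safety topic of special interest (protocol section 8.2.6). With about 87 participants per arm, a few carried-over cases could make up much of the table, and a reader could not tell which events followed treatment.

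**Working it through.** **1. Is there a comparison with baseline?**

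| SAP section | Measure | Rule against baseline |
|---|---|---|
| 4.5.2.1 | Adverse events | First occurrence or worsening after baseline |
| 4.5.3.4 | Vital signs | Crosses the limit and meets a change criterion |
| 4.5.5.9.1 | PHQ-9 | Shift table and three worsening outcomes, maximum value to maximum value |
| 4.5.5.9.2 | C-SSRS | None |

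**2. Who can carry ideation past baseline?** Criterion 14 concerns Questions 4 and 5 and behaviors within the past month; Categories 1 to 3 never exclude. Criterion 12 removes any lifetime suicide attempt. Criteria 11 and 13 remove significant unstable psychiatric illness within 2 years and a PHQ-9 score of 15 or more. Carry-over is therefore mainly Categories 1 to 3.

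**3. Which forms are in the window?** The default in SAP section 4.5 is "All data collected between randomization and the end date of study participation will be included", and the Safety Analysis Set holds treatment plus follow-up data. Both point to post-randomization forms. One edge remains: the Visit 3 form precedes randomization, which takes place at the end of that same visit (protocol section 6.3). A cut by calendar date would let a pre-dose form in.

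**4. How much could it matter?** The plan states no C-SSRS rate, count or power, so there is no figure to reproduce beyond the arm size, 261 / 3 = 87. The rates below are assumptions.

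- b = share positive before dosing, equal across arms: 2%, 5%, 10%.
- p = new-onset rate: 1% placebo, 5% tirzepatide.
- f = share of baseline-positive participants who report it again: 0.5 or 1.

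Reported rate = bf + (1 − bf)p. For b = 5%, f = 1: placebo 0.05 + 0.95 × 0.01 = 5.95%; tirzepatide 0.05 + 0.95 × 0.05 = 9.75%; risk ratio 9.75 / 5.95 = 1.64; risk difference 3.80 points.

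| b | f = 1: placebo vs tirzepatide | Risk ratio | Risk difference (points) | f = 0.5: risk ratio | Risk difference (points) |
|---|---|---|---|---|---|
| 0 | 1.00% vs 5.00% | 5.00 | 4.00 | 5.00 | 4.00 |
| 2% | 2.98% vs 6.90% | 2.32 | 3.92 | 2.99 | 3.96 |
| 5% | 5.95% vs 9.75% | 1.64 | 3.80 | 2.12 | 3.90 |
| 10% | 10.90% vs 14.50% | 1.33 | 3.60 | 1.64 | 3.80 |

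Counting baseline-negative participants only gives a risk ratio of 5.0 and a difference of 4.0 points at every b.

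At b = 5%, f = 1, the placebo arm would show 87 × 0.0595 = 5.2 participants with an event, of whom 87 × 0.05 = 4.35 are carried over.

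Exact Fisher power (two-sided 0.05, placebo 87 vs pooled tirzepatide 174), treatment-emergent among baseline-negative participants against all counted with f = 1:

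- b = 2%: 0.241 vs 0.186
- b = 5%: 0.220 vs 0.135
- b = 10%: 0.196 vs 0.101

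With no baseline ideation it is 0.250.

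**The case against.** **A reader might infer that screening forms are counted.** Protocol section 4.1 does list screening as a period ("Study GPHZ will consist of 3 periods: a 4-week screening period, followed by a 72-week treatment period"), but that describes the design, not an analysis window. The defaults in step 3 point the other way. So does the SAP's own usage: in the sections on vital signs, ECGs and liver enzymes, references to the entire study add follow-up, not screening. The restricted denominator fits the same reading. What remains is an ambiguity: the defaults yield where something else is specified, and this numerator has its own wording.

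**A reader might infer that old, resolved events count.** On the default reading they do not. Every form after Visit 1 asks only about the time since the last visit, so a resolved event would be answered no. This objection stands.

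**A treatment-emergent analysis already exists.** SAP section 4.5.5.9 summarizes treatment-emergent adverse events of depression and suicidality, and its event of special interest rests on the severe or serious ones, not on the C-SSRS. This limits the consequence. It does not replace a C-SSRS comparison: the SAP presents the questionnaire as additional to spontaneously reported events, and I found nothing requiring a C-SSRS yes to be recorded as an adverse event. The listing of all visits is optional.

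**Other counts also ignore baseline**, for example QTcF above 500 msec. That is true, but the protocol wording quoted above names the C-SSRS specifically.

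**No risk ratio is planned.** Section 4.5.5.9.2 asks for counts and percentages, with Fisher's exact test as the general default. On the difference scale the assumed carry-over changes little.

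**Conclusion.** The point holds as a minor one. The C-SSRS composites lack any comparison with baseline, so unchanged pre-existing ideation reported again after dosing is counted as an event. This departs from protocol section 8.2.5 and from the SAP's handling of PHQ-9. The window is also loosely worded and should be closed.

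The size cannot be established from the documents. In the illustration the direction is clear for the ratio, which moves toward 1, but the risk difference moves by at most 0.4 points. A reader might infer that a real drug signal would be masked. The documents do not support that: all rates are assumed, the exclusions narrow carry-over mainly to Categories 1 to 3, adverse events give a second route, and in the illustration power is at most 0.25 under either definition. The firmer reason to act is attribution: the table should show which events were new or worse after treatment began.

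The illustration assumes equal baseline prevalence and equal recurrence across arms, and no worsening beyond the new-onset rate.

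**What to change.** In SAP section 4.5.5.9.2:

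1. State that the event list and the three composites use C-SSRS forms completed after the first dose through the end of study participation.
2. Define the C-SSRS baseline as Visits 1 to 3, and state which recall period on the Visit 1 form is used, since the documents do not say.
3. Keep the any-postbaseline counts. Beside them, add a treatment-emergent row or a baseline-to-postbaseline shift table. Ideation is treatment-emergent if the maximum postbaseline category exceeds the maximum baseline category; behavior is treatment-emergent if reported postbaseline with none at baseline.
4. Base these additions on participants with a baseline form and at least one post-dose form.

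The cost is SAP wording and one derived flag. All the forms are already scheduled, so nothing new is collected. Free improvement, minor priority.

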#### **4.5.5.10.** Malignancy

Treatment-emergent malignancy will be considered as an AESI. The counts and percentages of participants with treatment emergent malignancy will be summarized by treatment and PT and ordered by decreasing frequency. Detailed searching criteria can be found in Appendix 6 (Section 6.6).

#### **4.5.5.11.** Renal Safety

Laboratory measures related to renal safety will be analyzed as specified for laboratory measurements in Section 4.5.3.6.

Two shift tables examining changes in renal function from baseline to postbaseline will be created. A min-to-min shift table of eGFR estimated by the Chronic Kidney Disease Epidemiology Collaboration (CKD-EPI) equation with units mL/min/1.73m², using categories ( $<30, \ge 30$  to  $<45, \ge 45$  to  $<60, \ge 60$ , and  $\ge 90$  mL/min/1.73m²). A max-to-max shift table of urine albumin-to-creatinine ratio (UACR), using the categories UACR <30 mg/g, 30 mg/g  $\le$  UACR  $\le 300$  mg/g, UACR  $\ge 300$  mg/g (respectively, these represent normal, microalbuminuria, and macroalbuminuria).

Mixed model repeated measure analyses for eGFR and UACR will be provided. Log transformation will be performed for UACR.

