## 4.4.3. Secondary and Exploratory Endpoints

Table GPHZ.4.2. Secondary and Exploratory Efficacy Measures for Improvement of Obesity-related Health Problems

Analysis variable	Criteria/Measures	Analysis set	Analysis method	Additional Information
Percentage of participants who met the following criteria at 72 weeks from BL	Improvement in at least 2 obesity related health problems for participants with BL BMI >27 and <35 kg/ m², or Improvement in at least 1 obesity related health problem for participants with BL BMI >35 kg/ m²	Efficacy analysis set	Logistic model in Section 4.4.2.2	Definition of endpoint: 4.4.1.3
	Improvement in at least 2 obesity-related health problems	Efficacy analysis set - participants with BL BMI ≥27 and <35 kg/m²	Logistic model in Section 4.4.2.2	Exploratory
	Improvement in at least 1 obesity-related health problem	Efficacy analysis set - participants with BL BMI ≥35 kg/m 	Logistic model in Section 4.4.2.2	Exploratory
Improvement in laboratory tests for obesity-related health problems (72 weeks)	Mean changes in OGTT 2-hr glucose at 72 weeks from BL	Efficacy analysis set - participants with IGT at BL	MMRM model in Section 4.3.2.1	
	Mean changes in fasting glucose at 72 weeks from BL	Efficacy analysis set - participants with IGT at BL	MMRM model in Section 4.3.2.1	
	Mean changes in Fasting lipids (TG) at 72 weeks from BL	Efficacy analysis set - participants with hyperlipidemia at BL	MMRM model in Section 4.3.2.1	
	Mean changes in HFF at 72 weeks from BL	Efficacy analysis set - participants diagnosed as NAFLD by MRI at BL	ANCOVA model in Section 4.4.2.1	
Improvement of IGT (72 weeks)	Proportion of participants who achieved improvements of IGT	Efficacy analysis set - participants with IGT at BL	Logistic model in Section 4.3.2.2	

Analysis variable	Criteria/Measures	Analysis set	Analysis method	Additional Information
Improvement of hyperlipidemia (72 weeks)	Proportion of participants who achieved improvements of hyperlipidemia	Efficacy analysis set - participants with hyperlipidemia at BL	Longitudinal logistic model in Section 4.4.2.3	
Improvement of NAFLD (72 weeks)	Proportion of participants who achieved improvements of NAFLD	Efficacy analysis set - participants diagnosed as NAFLD by MRI at BL	Logistic model in Section 4.3.2.2	Compare TZP 10 mg, 15 mg and pooled TZP doses with placebo

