Change in eGFR	Mean change from BL in • eGFR	Efficacy analysis set	MMRM model in Section 4.3.2.1	Exploratory objective added to protocol planned analyses

Analysis variable	Criteria/Measures	Analysis set	Analysis method	Additional Information
Shift in eGFR	Shift table of minimum baseline to minimum postbaseline	Efficacy analysis set		Exploratory objective added to protocol planned analyses
Change in UACR	Mean change from BL in UACR	Efficacy analysis set	MMRM model in Section 4.3.2.1	Exploratory objective added to protocol planned analyses
Improvement of hyperuricemia (72 weeks)	Proportion of participants who achieved improvements of hyperuricemia. Definition of improvement of hyperuricemia: Uric acid 7 mg/dL	Efficacy analysis set – participants with hyperuricemia at BL defined as uric acid > 7 mg/dL	Longitudinal logistic model in Section 4.4.2.3	Exploratory objective added to protocol planned analyses
Improvement of hypertension (72 weeks)	Proportion of participants who achieved improvements of hypertension. Definition of improvement of hypertension: Diastolic blood pressure <80 mmHg or Systolic blood pressure <130 mmHg.	Efficacy analysis set – participants with hypertension at BL defined as diastolic blood pressure ≥80 mmHg or Systolic blood pressure ≥130 mmHg.	Logistic model in Section 4.4.2.2	Exploratory objective added to protocol planned analyses
Change in NAFLD related parameters (24, 52, and 72 weeks)	Mean change from BL in  NAFLD fibrosis score	(1) Efficacy analysis set; (2) Efficacy analysis set - participants with NAFLD at BL	MMRM model in Section 4.3.2.1	Exploratory objective added to protocol planned analyses

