# 4.5.5.1. Exocrine Pancreas Safety

#### 4.5.5.1.1. Pancreatic Enzyme

Observed pancreatic enzyme data (p-amylase and lipase) will be summarized by treatment. The counts and percentages of participants with maximum postbaseline pancreatic enzyme value exceeding the following thresholds will be provided by baseline pancreatic enzyme value ( $\leq$  ULN, > ULN), and postbaseline:  $\leq$ 1 × ULN, (>1 to  $\leq$ 3) × ULN, (>3 to  $\leq$ 5) × ULN, (>5 to <10) × ULN, >10 × ULN.

Mean change for pancreatic enzymes may be evaluated using an MMRM model with log transformed (postbaseline measure/baseline measure), as response variable will be used to analyze each pancreatic enzyme.

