# 5. Sample Size Determination

Approximately, 348 participants will be screened to achieve 261 randomly assigned to study intervention (approximately 87 participants per intervention group).

The sample size determination assumes that evaluation of superiority of tirzepatide 10 mg and tirzepatide 15 mg to placebo will be conducted in parallel, each at a 2-sided significance level of 0.025 using a 2-sample t-test. Additionally, a difference of at least 11% mean body weight percentage reduction from randomization at 72 weeks for tirzepatide 10 mg and/or tirzepatide 15 mg compared with placebo, a common SD of 10%, and a dropout rate of 25% are assumed for statistical power calculations. Under the assumptions above, randomizing 261 participants in a 1:1:1 ratio to tirzepatide 10 mg, tirzepatide 15 mg, and placebo provides more than 90% power to demonstrate superiority of each tirzepatide dose to placebo.

The chosen sample size and randomization ratio also provides >90% power to establish superiority of tirzepatide 10-mg and/or tirzepatide 15-mg doses to placebo in terms of proportion of participants achieving at least 5% body weight reduction at 72 weeks, conducted in parallel using a Fisher's exact test, each at a 2-sided significance level of 0.025, assuming 25% of placebo-treated participants and 90% of tirzepatide-treated participants achieve the goal and a dropout rate of 25%.

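### UACR is log-transformed in the renal safety model but not in the efficacy and laboratory models, and other typically skewed markers are modelled untransformed: a cheap improvement

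*SAP*

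**What the plan says.** The SAP models UACR by a mixed model for repeated measures (MMRM) in several places.

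- **Section 4.5.5.11 (Renal Safety)** plans MMRM analyses for eGFR and UACR and adds: "Log transformation will be performed for UACR". It also sends renal laboratory measures back to Section 4.5.3.6.
- **Section 4.5.3.6 (Clinical Laboratory Evaluation)** names UACR among the tests to be analysed by MMRM and mentions no transformation.
- **Section 4.4.3, Table GPHZ.4.4 (efficacy)** has UACR twice. It is in the exploratory laboratory row at 24, 52 and 72 weeks, and again in its own row, "Mean change from BL in UACR", marked as added to the protocol-planned analyses. Both rows use the Efficacy Analysis Set (EAS) and the MMRM of Section 4.3.2.1.

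Section 4.3.2.1 is written for percent change in body weight and has no log step. The same model serves triglycerides (Table GPHZ.4.2: "Mean changes in Fasting lipids (TG) at 72 weeks from BL") and, in Table GPHZ.4.4, fasting insulin and hs-CRP.

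One other laboratory analysis uses logs. Section 4.5.5.1.1 says pancreatic enzymes may be evaluated by an "MMRM model with log transformed (postbaseline measure/baseline measure"). Section 4.9, which lists changes to the planned analyses, does not explain why the scales differ.

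**The concern.** A programmer following the SAP literally would fit UACR on the log scale for renal safety and on the original scale for efficacy. The two results could differ in size and in significance, and nothing says which one is to be interpreted.

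For a right-skewed marker, a few large values can dominate the mean and inflate its variance. If the drug acts proportionally, an analysis of untransformed change then spends power that a log analysis would keep. The same question arises for hs-CRP, fasting insulin and triglycerides. Leaving the scale unstated also means that it could be settled after the data are seen.

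**Working it through.** **1. The plan's own power figure.** SAP Section 5 gives "approximately 87 participants per intervention group", tested "each at a 2-sided significance level of 0.025 using a 2-sample t-test", with "a difference of at least 11% mean body weight percentage reduction from randomization at 72 weeks" and "a common SD of 10%, and a dropout rate of 25% are assumed for statistical power calculations".

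- Evaluable per arm: 87 × 0.75 = 65.25, taken as 65.
- Noncentrality: 11 / (10 × √(2/65)) = 6.27 on 128 degrees of freedom. Power is 99.996%.
- Responders, 25% versus 90%, Fisher's exact test at 0.025, 65 per arm: power above 99.99%.

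The stated figure of more than 90% reproduces. It concerns body weight only. No power, SD or skewness is given for any biomarker.

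**2. Inputs for the biomarkers.**

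- From the documents: 65 per arm for markers analysed in all participants. More than 60% are to have IGT (Protocol Section 4.1), so the IGT subset is at least about 87 × 0.60 × 0.75 = 39 per arm. Triglycerides are analysed in participants with baseline ≥150 mg/dL. The general two-sided level is 0.05 (SAP Section 4.1).
- Assumed: lognormal data; log SD *s*; baseline-to-Week-72 log correlation ρ (0.7 for UACR, 0.6 otherwise); a multiplicative effect *r*; 39 per arm for triglycerides, with an underlying median of 150 mg/dL.

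**3. Model.** Log baseline b ~ N(log m, s²). Log Week 72 value y = log m + ρ(b − log m) + g·log r + e, where e ~ N(0, s²(1 − ρ²)) and g = 1 for tirzepatide. One post-baseline value stands in for the Week 72 MMRM contrast. Two ANCOVAs are compared: raw change exp(y) − exp(b) adjusted for exp(b), and log change y − b adjusted for b. Each scenario has 3,000 trials, so the Monte Carlo standard error of a power figure is at most √(0.25/3000) = 0.9 points.

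**4. Results (power, raw versus log).**

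| Marker | n/arm | s | r | Raw | Log |
|---|---|---|---|---|---|
| UACR | 65 | 0.8 | 0.9 | 13.0% | 17.5% |
| UACR | 65 | 0.8 | 0.7 | 81.1% | 94.0% |
| UACR | 65 | 1.2 | 0.7 | 33.8% | 64.6% |
| UACR | 65 | 1.2 | 0.6 | 59.1% | 91.4% |
| hs-CRP | 65 | 1.0 | 0.7 | 46.3% | 70.2% |
| hs-CRP | 65 | 1.0 | 0.5 | 93.5% | 99.7% |
| hs-CRP | 65 | 1.2 | 0.6 | 52.8% | 85.6% |
| Insulin (IGT) | 39 | 0.5 | 0.7 | 94.3% | 96.9% |
| Insulin (IGT) | 39 | 0.5 | 0.8 | 59.7% | 67.4% |
| Insulin (IGT) | 39 | 0.7 | 0.7 | 66.5% | 79.5% |
| Triglycerides (≥150) | 39 | 0.35 | 0.8 | 91.3% | 93.3% |
| Triglycerides (≥150) | 39 | 0.5 | 0.8 | 63.6% | 67.5% |
| Triglycerides (≥150) | 39 | 0.35 | 0.7 | 100% | 100% |

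Over all scenarios run in this set, the loss on the raw scale is about 5–32 points for UACR (17.5 − 13.0 = 4.5 up to 91.4 − 59.1 = 32.3), 6–33 for hs-CRP, 3–13 for insulin and 0–4 for triglycerides.

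**5. A second set of assumptions** (between/within log SDs: UACR 0.8/0.5, hs-CRP 0.8/0.6, insulin 0.5/0.35, triglycerides 0.35/0.25; 65 per arm; one reduction per marker of 25%, 35%, 20% and 15% in that order) gave 46% versus 71%, 64% versus 88%, 68% versus 79%, and 75% versus 81%. The last is the 6-point upper end for triglycerides, and it ignores the ≥150 mg/dL restriction. With the restriction, the loss was 3 to 4 points.

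**6. Type I error and disagreement.** With no UACR effect (s = 1.2), the rejection rate was 4.0% raw and 4.9% log, so the gain does not come from a liberal test. At r = 0.70 for UACR, the two tests disagreed on significance in 15% (s = 0.8) to 37% (s = 1.2) of simulated trials.

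**The case against.** - **The direction is partly built in.** Lognormal data with a proportional effect is the model that the log ANCOVA fits. Additive effects were not examined. This stands: a loss of power cannot be shown from the documents, only illustrated.
- **Untransformed is read from silence.** The SAP never says that these markers stay on the original scale. Because 4.5.5.11 refers back to 4.5.3.6, its log sentence may be meant to govern that laboratory model too. That reading would settle the safety side, but it leaves the two efficacy rows unexplained.
- **Triglycerides.** A reader might infer that an important secondary endpoint loses material power. The figures do not support this: the loss is 0 to 6 points. Proportional change in triglycerides is also already covered by the responder endpoint, which counts a 30% reduction.
- **A SAP convention.** A reader might take the pancreatic-enzyme analysis as proof that the SAP logs skewed laboratory data as a rule. It is optional, and Section 4.5.3.6 lists the same enzymes without a transformation.
- **One scale, one answer.** A reader might expect a common scale to give a single UACR result. It would not. The efficacy rows use the EAS, which drops data beyond 7 days after the last dose. The safety model uses the Safety Analysis Set (SS), which includes follow-up regardless of adherence.
- **Endpoint wording.** Protocol and SAP define these endpoints as mean change from baseline, and a ratio of geometric means is a different summary. This stands, and it is why mean change should still be reported.

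**Conclusion.** The inconsistency for UACR is plain in the text: log scale in 4.5.5.11, and no transformation in 4.5.3.6 or in either row of Table GPHZ.4.4, with no reason given. The same silence covers hs-CRP, fasting insulin and triglycerides.

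The size of the cost is conditional on assumed log SDs, correlations and proportional effects. Within those assumptions the log scale did better in every non-null scenario short of saturation. The gain is worth having for UACR and hs-CRP, moderate for insulin and slight for triglycerides.

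UACR and hs-CRP are exploratory. Insulin and triglycerides are secondary and outside the alpha-controlled hypotheses. Nothing here touches the body-weight conclusions or their power. This is a cheap improvement, not an error that puts a main result at risk.

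**What to change.** 1. In Table GPHZ.4.4 and Section 4.5.3.6, state that UACR is analysed on the log scale with log baseline as covariate, matching Section 4.5.5.11.
2. Delete the duplicate UACR row in Table GPHZ.4.4.
3. Apply the same log model to hs-CRP and fasting insulin, and optionally to triglycerides, with results back-transformed to percent change.
4. Continue to report mean change from baseline on the original scale for these markers, so that the protocol's endpoint wording is kept.

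The cost is a few lines of SAP text, settled before unblinding. The modelled effect becomes a ratio, expressed as percent change, instead of an absolute difference. The EAS and SS estimates of UACR will be comparable but not identical, because they rest on different data.
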